### **Treatment period: Day 1 to Week 40/Week 44**

The Screening Visit and Baseline Visit (see [Table 8-1](#)) are the same visit.

One time re-assessment of patients is allowed, except for the purpose of capturing new BCVA or imaging assessments that previously failed to qualify the patient (except if image quality is poor and needs to be redone). As long as testing can be repeated within 14 days of the first screening, the other screening assessments do not need to be repeated. If rescreening is to occur beyond 14 days from the original Screening Visit date, then all screening procedures must be repeated. Medical judgment should be exercised to ensure that treatment of nAMD is not withheld in order for a patient to participate in the study.

After confirmation of eligibility, patients will be included in the study. A study visit schedule will be established at the time of Screening/Baseline Visit for all patients. All efforts should be made to adhere to the study visit schedule within a  $\pm 7$ -day window. For a given protocol visit, assessments can be performed on 2 consecutive days, provided both days are within the  $\pm 7$ -day window. Treatment (including at Screening/Baseline) is intended to be administered on the day of the study visit, or if this is not possible, within 3 days after the study visit when the per-protocol assessments will have taken place. If study visit assessments and the corresponding treatment occur on separate days, a repeat safety check-up should be performed prior to treatment of the eye and results documented in the source documents.

The Screening/Baseline Visit is defined as Screening/Baseline/Day 1. For all patients, the last potential study treatment will be at the Week 40 visit or at the Week 44 visit depending on whether patients receive the study treatment under the q8w or under the q12w schedule. The initiation phase starts on Day 1 and ends on Week 8. The q12w/q8w treatment regimen starts on Week 16 and ends on either Week 40 or Week 44 (see [Section 6.7.2](#)).

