Patients will receive 3 initial doses every 4 weeks (Day 1, Week 4 and Week 8) (loading phase), which should be at least 21 days apart, followed by treatment q12w with the possibility of adjusting to treatment q8w based on disease activity. Disease activity will be assessed based on investigator's judgment of visual acuity and anatomical parameters as provided in the guidance to the investigators, e.g. decrease of visual acuity and/or other signs of the disease (e.g. intraretinal fluid (IRF), subretinal fluid (SRF), sub-retinal pigmented epithelium (sub-RPE) fluid, retinal hemorrhage, central retinal thickness (CRT) increase, etc.). Disease activity will be assessed during the first q12w interval at Week 16. If no disease activity is observed by the investigator in the study eye, disease activity will be assessed every 12 weeks (at Week 20, Week 32 and Week 44). If disease activity is observed by the investigator in the study eye at any of these visits, the study treatment will be adjusted by the investigator to a q8w treatment regimen and will remain on this regimen until Week 40/Week 44 (see [Section 6.7.2](#)). Patients who require study treatment every 4 weeks after the initiation phase will be discontinued from further study treatment at the next visit.

The mandatory study visits during the treatment phase are Day 1, Week 4 and Week 8 (assessment of CNV lesion evolution during initiation phase), Week 12 (primary endpoint), Week 16 (first time to reach disease activity criteria and first possible treatment) and Week 48 (last efficacy assessment) visits. The timing of the interim visits between Week 16 and Week 48 will depend on the patient's injection regimen, i.e. q12w or q8w. No visits are planned between the injection visits (see [Section 6.7.2](#)).

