## 4.5 Risks and benefits

In a comprehensive Phase 3 program (see [Section 1.1](#)), consisting of 2 large, randomized, double-masked, multicenter, studies (RTH258-C001 and RTH258-C002) treatment with brolocizumab resulted in robust visual gains and superior anatomical outcomes compared to aflibercept, with the majority of patients maintained on an q12w dosing interval at 48 weeks, and the remainder maintained on an q8w dosing interval. Anatomical benefits and vision gains were maintained for 2 years.

The RTH258-C001 and RTH258-C002 studies successfully evaluated a novel treatment regimen, combining the prolonged duration of effect of brolocizumab with treatment frequency guided by disease activity. Reflecting clinical practice, investigators assessed disease activity using both visual function and anatomical disease parameters (e.g. retinal thickness and retinal fluid). Robust clinically meaningful results were observed for both functional and anatomical outcomes in a representative nAMD population over 48 weeks and sustained up to 96 weeks.

These benefits were consistent across subgroups (e.g. age, gender, race, Baseline visual acuity, Baseline retinal thickness, lesion type, lesion size, fluid status), replicated in 2 independent Phase 3 studies. Less than half of patients were identified with disease activity after the loading phase and most disease activity with adjustment of dosing interval was identified during the initial q12w interval; the vast majority of patients without disease activity during the initial q12w interval continued to be maintained on an q12w treatment interval for the remainder of the treatment period indicating the benefit of early treatment monitoring in maintaining long-term efficacy. These results thus addressed the unmet medical need of delivering efficacy comparable to standard of care, while reducing the treatment and monitoring burden.

Sustained visual acuity is a key validation for the q12w/q8w regimen, as it relates to the unmet medical need of maintaining patients' long-term vision.

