### q12w/q8w treatment phase

The mandatory visit at Week 12 will be performed to evaluate the primary endpoint of the study. No treatment will be administered at Week 12; the next visit will take place at Week 16. Disease activity will be assessed at Week 12 for endpoint assessment purposes.

The q12w/q8w treatment phase starts at Week 16 and is defined as follows:

- Following Week 8, treatment intervals will be either 8 weeks or 12 weeks. A patient must be discontinued from further study treatment if treatment is required more frequently, i.e., every 4 weeks.
- The first assessment of disease activity during this phase will be performed at the Week 16 visit by the investigator.
- Based on investigator's judgment of visual and/or anatomic outcomes, the treatment can be adjusted by the investigator to a q8w treatment regimen if there is disease activity as

provided in the guidance to the investigators, e.g. decrease of visual acuity and/or other signs of the disease (e.g. IRF, SRF, sub-RPE fluid, retinal hemorrhage, CRT increase, etc.).

- The disease activity assessment is performed at each subsequent visit by the investigator.
- If disease activity is identified, the patient will be reassigned to receive injections q8w thereafter up to Week 40/Week 44.
- Regardless of treatment administration, Week 16 and Week 48 visits are mandatory.
- The timing of the interim visits between Week 16 and Week 48 will depend on the patient's injection regimen, i.e. q12w or q8w.
- No visits are planned between the injection visits.
- The last potential study treatment may be administered at the Week 40 visit or at the Week 44 visit according to the patient's treatment regimen.
- A disease activity assessment will also be performed at the Week 48/EOS visit; however, no study treatment will be administered.

The different types of visits occurring through the study are summarized in [Table 6-3](#) with a description of when disease activity assessment and treatment take place.

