### **Disease activity criteria**

Disease activity criteria will be assessed by the investigator based on whether nAMD is still active or has been re-activated. Guidance for the investigator are as follows (disease is active if at least one of the following criteria is observed by the investigator):

- BCVA decrease  $\geq 5$  letters from the best value since Baseline due to disease activity.
- Any significant increase in CRT (based on investigator assessment).
- Retinal hemorrhage.
- Intraretinal fluid or SRF due to disease activity (degenerative cysts allowed).
- Increase of sub-RPE fluid.

These criteria are for guidance only, the investigator may define disease activity based on his/her own assessment.

Anatomic parameters measured by OCT-A and by SD-OCT will be analyzed by a CRC. The main aim of the CRC analysis is to confirm anatomic features from OCT-A and SD-OCT images for the primary endpoint. The CRC will have no involvement in assessment of disease activity, which is solely the investigator's responsibility.

A patient who misses Week 16 will undergo the disease activity assessment at Week 20 as he/she would have done if the visit had not been missed. If, however, a patient misses any of the following disease activity assessment visits (Week 20, Week 32) then the patient will be assumed to have met the disease activity criterion at the missed visit and will be reassigned to an q8w regimen up to study exit.

If a patient misses Week 12, then the Week 8 values will be applied as the reference for disease activity assessments up to and including Week 44.

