 Intraocular pressure (IOP) will be assessed in the study eye, pre-dose and post-dose at every injection. The same method of tonometry has to be used through the whole study. Close monitoring of IOP should be performed by the investigator for any non-transient elevation in IOP ( $\geq 25$  mmHg). Intravitreal injection is not recommended unless normalization of the IOP has been achieved. Post-dose IOP should be assessed within 60 minutes after injection and if  $\geq 25$  mmHg, assessment should be repeated until back to normal. Monitoring of the optic nerve head perfusion after injection may be appropriate, at the discretion of the investigator. Results of these procedures will be recorded as appropriate in the source documents and if the findings constitute an AE, it should be recorded in the eCRF.

 Additional ophthalmic examinations and images will be performed in case of any signs of intraocular inflammation (IOI), retinal vasculitis, and/or retinal vascular occlusion.

 A telephone follow-up on safety should be performed one week after the first injection (a window for the phone call is +7 days). From the second injection onwards, similar phone calls should be made at investigator's discretion per local practice.

 The week 48 EOS assessments only apply to patients who completed the study per protocol. The assessments are not required for patients who have undergone ETD assessments and continued in the study without study treatment.

 ETD: Early treatment discontinuation applies to patients who discontinue early from study treatment and continue in the study. The assessments should be performed 4 weeks after the last injection of study drug. This can occur at any time point.

 For patients who continue in the study after ETD and up to Week 48 (end of study) while patient is on standard of care. Additional safety assessments and imaging can also be performed if required, as per investigators discretion. In addition, after ETD, subjects are not required to attend the mandatory visits at Week 12 and Week 48. The last visit should be at week 48. This can occur at any time point.

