## 9 Study discontinuation and completion

### 9.1 Discontinuation

#### 9.1.1 Discontinuation of study treatment

Discontinuation of study treatment for a patient occurs when study treatment is stopped earlier than the protocol planned duration, and can be initiated by either the patient or the investigator.

The investigator must discontinue study treatment for a given patient if he/she believes that continuation would negatively impact the patient's well-being.

The investigator and/or referring physician will recommend the appropriate follow-up medical care, if needed, for all patients who are prematurely withdrawn from the study.

Study treatment must be discontinued under the following circumstances:

- Patient requires treatment on a q4w interval after the initiation phase, i.e., after the three monthly injections at Baseline, Week 4, and Week 8, followed by the first interval extension
- Patient develops intraocular inflammation, including retinal vasculitis and/or retinal vascular occlusion
- Patient/guardian decision
- Pregnancy
- Use of prohibited treatment
- Any situation in which study participation might result in a safety risk to the patient

If premature discontinuation of study treatment occurs, the following should be done as appropriate:

- The investigator should make a reasonable effort to understand and document the primary reason for the patient's premature discontinuation of study treatment using the appropriate eCRF page.
- Patients who prematurely discontinue study treatment for any reason should return 4 weeks after last study treatment to perform the assessments for early treatment discontinuation (ETD). Please refer to [Table 8-1](#), except for patients who withdraw their consent from the study and do not wish to do so (refer to [Section 9.1.2](#)).
- After these assessments are performed, patient can be switched to standard of care (SOC) anti-VEGF IVT as per investigators discretion. IVT injection is contraindicated in patients with active intraocular or periocular infections and in patients with active intraocular inflammation; therefore, the investigators must verify that these conditions are not present in the study eye prior to every injection.
- After premature study treatment discontinuation, at a minimum till week 48, in abbreviated visits, the following data should be collected at clinic visits or via telephone/email contact:
  - New/concomitant treatments

- Adverse events/Serious Adverse Events
- BCVA

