2.6 Analysis of secondary efficacy objectives

2.6.1 Secondary endpoints

2.6.1.1 Oct-A long-term effects

The first secondary endpoint is the percentage change in CNV lesion area (mm²) measured by OCT-A for nAMD patients from Baseline to Week 48. Descriptive statistics (n, mean, std, median, min and max) for the change in CNV lesion (actual value, change from Baseline, percentage change from Baseline) will be presented based on observed data by visit. Furthermore, a 2-sided 95% CI using Student's t-distribution will be provided.

The number and percentage of lesion type (predominantly classic, minimally classic and occult) will be presented by visit.

The above analysis will be done only on the study eye. The analysis will be performed on the FAS.

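### By-visit rows for Weeks 20 to 44 hold different patients, because the visit schedule follows the switch to q8w; pooled rows can therefore move through attendance alone

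*SAP*

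**What the plan says.** **Visits.** Protocol section 3 makes only Day 1 and Weeks 4, 8, 12, 16 and 48 mandatory. For a patient without activity at Week 16, "disease activity will be assessed every 12 weeks (at Week 20, Week 32 and Week 44"). A patient with activity moves to q8w and stays there. Section 6.7.2 adds: "No visits are planned between the injection visits".

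**What triggers a switch.** The guidance in section 6.7.2 lists BCVA loss, CRT increase, haemorrhage, fluid ("Intraretinal fluid or SRF due to disease activity (degenerative cysts allowed")) and more sub-RPE fluid, but the investigator may use his or her own judgment. A missed Week 20 or Week 32 visit also counts as activity.

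**Tables.** In the SAP Addendum, lesion-area statistics "will be presented based on observed data by visit", with a t-based CI (2.6.1.1). CSFT (2.6.1.2.1), fluid (2.6.1.2.2), dryness with Clopper-Pearson CIs (2.6.1.2.3), BCVA (2.6.1.4) and disease activity (2.6.1.6) are also by visit on the FAS. None of these sections mentions regimen. Table 2-1 sets an analysis window every four weeks up to Week 48, and unscheduled visits are kept out of by-visit tables (2.1.2).

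**Discontinuation.** For the ETD visit, Table 8-1 of the protocol says: "The assessments should be performed 4 weeks after the last injection of study drug. This can occur at any time point". Afterwards, under section 9.1.1, "the following data should be collected at clinic visits or via telephone/email contact"; BCVA is one of the items. Protocol section 12.4.3 censors efficacy data when study treatment stops. SAP section 2.1.1 instead speaks of efficacy data being used at that time.

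**The concern.** Several secondary endpoints are defined by visit up to Week 48, so readers will look down the rows as a time course. Between Weeks 20 and 44 adjacent rows describe different patients. Patients were sorted into those rows largely by earlier disease activity, judged on the same kind of outcomes that the rows report. A drop or rise from one week to the next may then reflect who was due that week and not any change in the disease. The by-visit CIs add to this: an interval around a row of switched patients looks like an interval for the whole cohort.

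**Working it through.** **1. Who is planned at each week** (protocol sections 3 and 6.7.2; no assumptions needed)

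| Switch triggered at | Planned visits between Weeks 16 and 48 |
|---|---|
| never (or only at Week 44) | 20, 32, 44 |
| Week 16 | 24, 32, 40 |
| Week 20 | 20, 28, 36, 44 |
| Week 32 | 20, 32, 40 |

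Reading by week:
- Week 24: Week 16 switchers only.
- Weeks 28 and 36: Week 20 switchers only.
- Week 40: Week 16 and Week 32 switchers only.
- Week 20 omits Week 16 switchers; Week 32 omits Week 20 switchers; Week 44 omits Week 16 and Week 32 switchers.

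A visit from Week 12 to Week 48 made within ±7 days of schedule never falls in another week's Table 2-1 window, so windowing does not mix the groups.

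**2. Inputs for size.** The plan's total is N = 189/0.90 = 210. It gives no switch rate. On the earlier phase 3 studies, protocol section 4.5 says only: "Less than half of patients were identified with disease activity after the loading phase", mostly found in the first q12w interval. I therefore assume four sets of conditional switch probabilities at Weeks 16, 20 and 32, no dropout, attendees as denominator, and the same outcome gap for all switch times.

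**3. Formula.** S = total share switched. k = (share of ever-switched among attendees) − S. Row value minus cohort value = k × gap, where gap = switched minus never-switched.

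Worked case, 20/12/8%: Week 16 switchers 0.200; Week 20 switchers 0.80 × 0.12 = 0.096; Week 32 switchers 0.80 × 0.88 × 0.08 = 0.056; never 0.648; S = 0.352.
- Week 20: (0.096 + 0.056)/0.80 − 0.352 = −0.16
- Week 24: 1 − 0.352 = +0.65
- Week 32: (0.200 + 0.056)/0.904 − 0.352 = −0.07
- Week 44: 0.096/(0.096 + 0.648) − 0.352 = −0.22

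| Assumed switching, % | 15/8/4 | 20/12/8 | 30/15/10 | 35/15/8 | Expected n |
|---|---|---|---|---|---|
| S, % | 25 | 35 | 46 | 49 | |
| k, Week 20 | −0.13 | −0.16 | −0.23 | −0.27 | 137–179 |
| k, Weeks 24, 28, 36, 40 | +0.75 | +0.65 | +0.54 | +0.51 | 32–74; 14–22; 14–22; 38–83 |
| k, Week 32 | −0.05 | −0.07 | −0.06 | −0.05 | 188–196 |
| k, Week 44 | −0.17 | −0.22 | −0.30 | −0.33 | 127–172 |

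Protocol section 3 also places the last possible treatment "at the Week 40 visit or at the Week 44 visit depending on whether patients receive the study treatment under the q8w" or the q12w schedule. If that means q8w patients have no Week 44 visit, k at Week 44 becomes −0.25 to −0.49.

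**4. Illustration, no patient changing.** Suppose fluid is present in 60% of switched and 20% of never-switched patients throughout. The cohort value is 30–40%. Attendee rows read 25–29% (Week 20), 60% (Weeks 24, 28, 36, 40), 28–37% (Week 32) and 23–27% (Week 44). With the whole FAS as denominator, the Week 24 row would instead read 9–21% (for example 0.60 × 0.15 = 9%).

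**5. ETD visits.** A q12w patient who stops after the Week 20 injection has an ETD visit at about Week 24. If 2–5% did so and the visit were windowed, k at Week 24 would be +0.44 to +0.66.

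**6. Windows (separate point).** Visits are scheduled from the baseline visit, but study day counts from the first injection, which may be d = 0–3 days later. An on-time visit at week w therefore falls on study day 7w + 1 − d ± 7.
- Week 4, d = 0: Days 22–36 against a window of 22–34, so 35 and 36 have none. d = 1: 21 and 35. d = 2: 20 and 21. d = 3: 19–21.
- Week 8: the same, 28 days later (63 and 64 for d = 0; 47–49 at the early end).
- Week 16, d = 0: Day 120.
- No other week has a gap.

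**The case against.** **Row size will be visible.** SAP section 2.1 requires n and the number missing for every continuous summary, so a fall from about 190 to about 20 would show. Section 2.4.1 tabulates injections and missed visits by visit, and section 2.6.1.5 gives the number on q8w. This stands, and a careful reader could partly infer the composition. But n shows that a row is smaller, not who is in it. For percentages the denominator is not stated.

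**A regimen split changes few numbers.** Only Weeks 32 and 44 mix patients already on q8w with patients still on q12w, and k at Week 32 is small. That is right. At the other weeks the gain is a correct label.

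**An obvious split does not cure the problem.** If columns use the regimen known before each visit, the q12w column loses switchers over time. In the illustration it goes from 24.7–29.4% (Week 20) to 21.6–24.0% (Week 32) to 20.0% (Week 44) with no patient changing. This stands, and it is why the groups must be fixed by switch time.

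**A discontinuation rule exists.** A reader might infer that the plan is silent on data collected after treatment stops. It is not: protocol section 12.4.3 censors them. What is open is the ETD visit itself, and how the SAP's differently worded rule fits.

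**Part of the plan is unseen.** Section 2.7 of the SAP and the table shells are not available, so a split there cannot be ruled out.

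**Conclusion.** The point holds as an improvement to descriptive tables. Who is planned at Weeks 20–44 follows from the protocol alone, and the visible SAP text pools those rows without a regimen split, with by-visit CIs for lesion area and dryness.

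The size is conditional. It needs a switch rate and an outcome gap, and the documents give neither. Under the assumed rates, a gap of 10 points puts the Week 24 row 5.1–7.5 points from the cohort value; a gap of zero puts it nowhere.

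Three stronger readings are tempting and not supported. One is that the main results are biased: the Week 12 primary and Week 48 change endpoints use visits planned for all patients on treatment, so this selection does not reach them. Another is that the Week 24, 28, 36 and 40 rows will contain switched patients without exception: that is true of planned visits, but an ETD visit could add a few others. The third is that patients are sorted only on earlier outcome values: a missed Week 20 or 32 visit also moves a patient to q8w.

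The window gaps are real but minor. How many visits fall on those days is unknown.

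**What to change.** 1. **Weeks 20–44:** show these outcomes by fixed switch-time group (never switched, switched at Week 16, Week 20, Week 32), with n. Small groups may be combined; expected sizes are about 14–22 for Week 20 and 7–12 for Week 32 switchers. Label the groups as descriptive and defined by later regimen. Reading across weeks then follows the same patients. If groups by regimen known before the visit are preferred, footnote that the q12w column loses switchers and is not a trend.
2. **Pooled rows:** keep them, cohort-level CIs and trend statements to Weeks 4, 8, 12, 16 and 48. If pooled Weeks 20–44 rows are kept for the by-visit endpoint, footnote who is scheduled and do not join them into one curve.
3. **Denominator and discontinuation:** use attendees as the percentage denominator. Apply the censoring rule of protocol section 12.4.3, reconcile SAP section 2.1.1 with it, and say whether the ETD visit is windowed.
4. **Table 2-1, separately:** use Day 19–36 (Week 4), 47–64 (Week 8) and 99–120 (Week 16). These close the gaps without overlap. They decide only which assessments are tabulated, not when injections are given.

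The cost is SAP wording and layout, using data already collected. The downside is a few more, smaller tables. There would also be fewer by-visit CIs than protocol section 12.5.1 and SAP sections 2.6.1.1 and 2.6.1.2.3 foresee, which should be recorded in SAP section 4.
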